4.6 Investigational Product Exposure

[figure not shown]
The number of doses received, amount of daxdilimab received, durations of daxdilimab exposure, and total person years of exposure will be summarized for this OLE study using OLE safety analysis set, and together with Study RECAST SLE using the full analysis set, respectively. The number and percentage of participants treated ≥ 12 weeks, ≥ 24 weeks, ≥ 36 weeks, and ≥ 48 weeks will also be provided.

- Durations of daxdilimab exposure is defined as:
 - OLE study: last dose date in OLE study + 28 first dose date in OLE study + 1;
 - Any daxdilimab exposure: last dose date in OLE study + 28 first daxdilimab dose date in study RECASE SLE or study OLE + 1.
- Person years of exposure (PYE) = durations of exposure / 365.25.
- The amount of study daxdilimab exposure: if a participant received partial dose at a dosing visit, then the amount of daxdilimab at that dosing visit will be estimated based on the actual volume administered.

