5 STUDY POPULATION

5.1 Inclusion Criteria

All subjects must meet all of the following criteria to be eligible for study participation:

1. Willing and able to understand and provide written informed consent (as described in Appendix 1, [Section 10.1.3](#)) prior to any study-related procedures and to comply with all study requirements and complete study assessments.
2. Must have qualified for and received IP (daxdilimab or placebo) and complete the treatment period (through Day 337) in the RECAST SLE study. Subjects who discontinued early from IP in RECAST SLE are not eligible for this study.
3. Women of childbearing potential must have a negative urine pregnancy test on Day 1. Women of childbearing potential are defined as those who are not surgically sterile (ie, surgical sterilization includes bilateral salpingectomy, bilateral oophorectomy, or hysterectomy) or those who are not postmenopausal (defined as 12 months with no menses without an alternative medical cause and a follicle-stimulating hormone [FSH] within the postmenopausal range as established by the central laboratory during the

screening period of the RECAST SLE study, unless on postmenopausal hormone replacement therapy).

If a female subject becomes postmenopausal during the study (ie, 12 months with no menses without an alternative medical cause, unless on postmenopausal hormone replacement therapy), a FSH test will be performed at the central laboratory. If the FSH level is within the postmenopausal range, the female subject will not be required to use contraception after that.

Women of childbearing potential who are sexually active with a nonsterilized male partner must agree to use a highly effective method of contraception from signing of the ICF and must agree to continue using such precautions through the end of the study follow-up or 3 months (approximately 5 half-lives) following the last dose of IP in the case of early withdrawal from the study, and refrain from egg retrieval/egg donation during this period. After this point, a decision about contraception should be made by the subject and her regular healthcare providers. Female subjects who participate in the SLE OLE are expected to maintain the same form of contraception they used during the RECAST SLE study. Effective methods of contraception are listed in Appendix 3, [Section 10.3](#).

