4.4.2 Full Analysis Set

The full analysis set is defined as participants who were randomized and received any dose of IP in study RECAST SLE. Participants will be analyzed according to the treatment to which they were randomized in RECAST SLE study. The exploratory efficacy analyses will be based on the full analysis set.

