4.4.3 Any Daxdilimab Analysis Set

The any daxdilimab analysis set includes all participants who receive at least one dose of daxdilimab in study RECAST SLE or this OLE study. The any daxdilimab analysis set will be used for the adverse events and immunogenicity analyses.

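### The combined RECAST + OLE exposure summary (SAP 4.6) counts never-exposed placebo participants, unlike the combined adverse event rates, and its duration rows do not separate exposure beyond 48 weeks

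*SAP*

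**What the plan says.** SAP 4.6 plans two exposure summaries. One covers the OLE alone in the OLE safety analysis set. The other covers the OLE "together with Study RECAST SLE using the full analysis set, respectively". Each reports dose count, amount, duration and total person-years. The section also asks for the number and percentage treated "≥ 12 weeks, ≥ 24 weeks, ≥ 36 weeks, and ≥ 48 weeks" and gives no separate rows for the combined summary.

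SAP 4.4.2 states: "The full analysis set is defined as participants who were randomized and received any dose of IP in study RECAST SLE". It adds: "Participants will be analyzed according to the treatment to which they were randomized in RECAST SLE study". In RECAST, IP means either arm, as Protocol 5.1 shows: "Must have qualified for and received IP (daxdilimab or placebo) and complete the treatment period (through Day 337) in the RECAST SLE study". The same criterion closes the OLE to early stoppers: "Subjects who discontinued early from IP in RECAST SLE are not eligible for this study".

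For the combined safety results the SAP uses another population. SAP 4.4.3 says: "The any daxdilimab analysis set will be used for the adverse events and immunogenicity analyses". SAP 4.9.1 computes the exposure-adjusted incidence rates in that set and refers back to 4.6 for the definition of person-years.

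**The concern.** A placebo participant who stopped IP early in RECAST cannot enter the OLE and never receives daxdilimab, but still belongs to the full analysis set. The combined daxdilimab exposure table therefore counts people with no daxdilimab exposure. A reader who sets it beside the combined adverse event table will find different denominators.

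The duration rows raise a second problem. They suit a 48-week study, but the combined summary spans two such periods. The primary objective is long-term safety, so the number of people exposed well beyond one year is basic context for the adverse event results. No row gives it.

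**Working it through.** **Inputs.** 195 randomized in RECAST, with 20% assumed to discontinue (SAP 2.3). First OLE dose at RECAST Week 48, which is Day 48 × 7 + 1 = 337 (Protocol 4.1, 5.1). OLE doses at Weeks 0, 12, 24, 36 and 48 (Protocol 6.1). Duration = last OLE dose date + 28 − first daxdilimab dose date + 1 (SAP 4.6, reading a minus sign before the first-dose term). The RECAST allocation is not in the documents, so I assume a placebo share of 25% to 50%.

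**The plan's own figure.** 195 × (1 − 0.20) = 156, which matches the approximately 156 in SAP 2.3.

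**Duration.** With the first daxdilimab dose on RECAST Day 1 and rollover on schedule, a last OLE dose at OLE Week w falls on day 337 + 7w. The duration is 337 + 7w + 28 − 1 + 1 = 365 + 7w days. For the OLE alone the last dose falls on day 1 + 7w, which gives 29 + 7w days.

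| Last OLE dose | Combined, RECAST-daxdilimab | OLE only |
|---|---|---|
| Week 0 | 365 d (52.1 wk) | 29 d (4.1 wk) |
| Week 12 | 449 d (64.1 wk) | 113 d (16.1 wk) |
| Week 24 | 533 d (76.1 wk) | 197 d (28.1 wk) |
| Week 36 | 617 d (88.1 wk) | 281 d (40.1 wk) |
| Week 48 | 701 d (100.1 wk) | 365 d (52.1 wk) |

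Every combined value exceeds 48 weeks (336 days). A first OLE dose as early as Day 308 would already reach the limit, since 308 + 28 − 1 + 1 = 336. A former placebo participant with all five OLE doses (365 days) falls in the same row, so in a pooled column the top row mixes about one year with nearly two. The OLE-only values spread across the existing rows.

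**Never-exposed participants.** Assuming 20% discontinuation in each arm and that every completer enters the OLE:

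- 25% placebo: 195 × 0.25 × 0.20 = 9.75, or 5% of 195.
- 50% placebo: 195 × 0.50 × 0.20 = 19.5, or 10% of 195.

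Within the placebo column the share is 20% whatever the allocation. Removing these people leaves 185.25 or 175.5, so a percentage in a pooled column rises by a factor of 195/185.25 = 1.05 or 195/175.5 = 1.11. Completers who decline the OLE would add to the never-exposed count.

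**A gap that the change of set exposes.** The combined duration ends at the last OLE dose, so it has no value for RECAST-daxdilimab participants who never entered the OLE. On the same assumptions they number 195 × 0.75 × 0.20 = 29.25 to 195 × 0.50 × 0.20 = 19.5. They belong to both the full analysis set and the any daxdilimab set, so changing the set alone does not give them a duration.

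**The case against.** The strongest reply is that the combined summary is more than its duration rows. It reports duration, doses, amount and person-years, and under SAP 4.1 continuous variables get median, quartiles and maximum. Exposure near 100 weeks would show there. This stands. A reader might infer that the table cannot show long-term exposure at all; the documents do not support that, because only the categorical rows lack resolution. Nor does every RECAST-daxdilimab participant pass 48 weeks at a first OLE dose: early stoppers have no OLE dose, so the statement is limited to those who roll over.

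The full analysis set is also analyzed by randomized arm. If 4.6 follows that rule, never-exposed people sit in the placebo column and leave the daxdilimab column untouched. This stands too, and it confines the problem to the placebo column and any total. By-arm display moves these people without removing them.

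A reader might further infer that the adverse event rates are diluted by never-exposed people. They are not: those rates use the any daxdilimab set, and never-exposed people contribute no person-years. Because OLE entry requires prior RECAST IP, the two sets differ essentially by the placebo-only participants.

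Finally, disposition (SAP 4.5) uses the full analysis set, so matching it is a possible motive, and presentation detail is deferred to the Statistical Programming Plan, which is not among the documents. But 4.6 itself names the set and the rows, and an exposure table mainly has to support the safety rates.

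The continuous statistics do not cure the denominator problem. Never-exposed people enter them either as zeros, which lowers the mean and can lower the median and quartiles, or as missing, so that n falls short of N. SAP 4.6 does not say which.

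**Conclusion.** The point holds within limits. As written, the combined exposure percentages include never-exposed people in the placebo column and any total, about 10 to 20 of 195 (5% to 10%), and the table does not match the population behind the combined adverse event rates. That count rests on an assumed 25% to 50% placebo share, the plan's 20% discontinuation applied equally to both arms, and full rollover of completers.

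The finding on the duration rows needs no allocation assumption. For RECAST-daxdilimab participants who roll over on schedule, the whole range from 52.1 to 100.1 weeks falls in one row.

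No hypothesis test is involved and the adverse event denominators are unaffected. This is a matter of consistency and resolution in a main supporting safety table, and it should be corrected because the repair is cheap.

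**What to change.** In SAP 4.6:

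1. For the combined RECAST + OLE summary, replace the full analysis set with the any daxdilimab analysis set, shown overall and by RECAST arm.
2. For that summary, add duration rows above 48 weeks, for example ≥ 60, ≥ 72, ≥ 84 and ≥ 96 weeks. These cut-points are a suggestion; they separate the five possible last OLE doses in the table above.
3. Define the combined duration from the first daxdilimab dose to the last daxdilimab dose in either study, so that RECAST-daxdilimab participants who never entered the OLE have a duration and person-years.
4. Leave the OLE-only summary and its existing rows unchanged.

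The cost is a few wording changes in one SAP section and some extra table rows. The analysis set is already defined and the dosing dates are already collected.

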5.4 Screen Failures

A screen failure occurs when a subject who has consented to participate in the clinical study is not subsequently entered/enrolled in the study. A minimal set of screen failure information is required to ensure transparent reporting of screen failure subjects, to meet the Consolidated Standards of Reporting Trials publishing requirements, and to respond to queries from regulatory authorities. Minimal information includes screen failure details, eligibility criteria, and any SAEs.

Individuals who do not meet the criteria for participation in this study (screen failure) may not be rescreened. These subjects will remain in and complete the SFU period of the RECAST SLE study.

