4.4.4 Pharmacokinetic Analysis Set

The PK analysis set is defined as participants who received any dose of daxdilimab in this OLE study and have at least one measurable PK concentration post dose. The PK analyses will be based on PK analysis set.

4.5 **Participant Disposition**

A summary of participant disposition will be presented for the full analysis set using the categories presented below.

- Completed Week 48 in RECAST SLE
- Enrolled in OLE
- Enrolled but not treated
- Enrolled and treated
- Completed treatment
- Discontinued treatment with reasons
- Completed trial
- Discontinued trial with reasons

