4.8 Exploratory Efficacy Analyses

4.9 Safety Analyses

4.9.1 Adverse Events

Adverse events (AEs) collected in this OLE study will be summarized separately using the OLE safety analysis set and together with the AEs collected in study RECAST SLE using the any daxdilimab analysis set overall and by treatment group. Table 4 presents the definition of treatment-emergent adverse event (TEAE) for reporting purposes.

Study	Definition
OLE	A TEAE is defined as any AE with an onset date on or after the first dose date in the OLE study.

Study	Definition
OLE + RECAST SLE (Any daxdilimab exposure)	A TEAE is defined as any AE with an onset date on or after the first daxdilimab dose date (either in OLE or RECAST SLE study)

Table 4Definition of TEAEs

AEs will be coded using the most recent version of MedDRA. All TEAEs will be summarized overall and by MedDRA system organ class (SOC) and preferred term (PT), by severity and by relationship to daxdilimab. Specific AEs will be counted once for each participant for calculating rates, but all events will be presented in participant listings. In addition, if the same AE occurs multiple times within a particular participant, the highest severity and level of causality will be reported.

In addition, since the duration of exposure to daxdilimab is shorter for the participants who received placebo in the RECAST SLE study, the PYE adjusted incidence rate for the number of participants who experienced TEAE will be included in the combined summary of OLE + RECAST SLE using any daxdilimab analysis set. Refer to Section 4.6 for definition of PYE.

An overall summary table will be showing the number and percentage of participants with at least one event in any of the following categories:

- TEAE
- Treatment-emergent serious adverse event (TESAE)
- TEAE resulting in death
- Grade 3 or higher TEAE using CTCAE v5.0
- TEAE leading to discontinuation of daxdilimab
- Serious and/or grade 3 or higher TEAE
- Daxdilimab related TEAE
- Daxdilimab related TESAE

The following AE summaries will also be provided by SOC and PT:

- TEAEs
- TEAEs resulting in death
- Grade 3 or higher TEAEs using CTCAE v5.0
- TEAE leading to discontinuation of daxdilimab
- Daxdilimab related TEAE
- TESAEs
- Daxdilimab related TESAE

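### The exposure definition behind the combined OLE + RECAST TEAE rate leaves person-time undefined for participants given daxdilimab only in RECAST, and it stops before TEAE counting does

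*SAP*

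**What the plan says.** - **Who is in the rate.** SAP 4.4.3: "The any daxdilimab analysis set includes all participants who receive at least one dose of daxdilimab in study RECAST SLE or this OLE study". Participants whose only daxdilimab was in RECAST therefore belong.
- **Which events count.** SAP 4.9.1, Table 4: for the combined summary, any AE starting on or after the first daxdilimab dose in either study. No end date is given. Protocol 8.4.4 collects AEs up to the final visit, which is Day 393 (Protocol 7.3), 56 days after the Week 48 dose.
- **The rate.** SAP 4.9.1: "the PYE adjusted incidence rate for the number of participants who experienced TEAE will be included in the combined summary". The stated reason is that former-placebo participants have shorter daxdilimab exposure. For the denominator it says "Refer to Section 4.6 for definition of PYE".
- **The denominator.** SAP 4.6: "Any daxdilimab exposure: last dose date in OLE study + 28" days, counted from the first daxdilimab dose in either study and divided by 365.25. The start names both studies; the end names only the OLE.
- **Who has no OLE dose.** Protocol 5.1: "Subjects who discontinued early from IP in RECAST SLE are not eligible for this study". Protocol 5.4, on OLE screen failures: "These subjects will remain in and complete the SFU period of the RECAST SLE study". SAP 4.5 also lists a disposition category "Enrolled but not treated".

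**The concern.** The rate exists to put groups with different lengths of daxdilimab exposure on a fair footing. As written it has two faults.

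First, it cannot be computed for part of its own analysis set. A programmer would have to choose between keeping these participants' events with no person-time, adding their RECAST person-time, or losing them through a missing duration. The last choice would remove the daxdilimab-treated early discontinuers from RECAST, a group in which stopping because of an AE would be found.

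Second, events are counted over a longer window than person-time. The extra window is the same number of days for completers in both groups but a larger share of the shorter exposure. The rate is therefore overstated more in the former-placebo group, whose shorter exposure is the reason for the adjustment.

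**Working it through.** **Inputs from the documents.** 195 randomized in RECAST and 20% premature discontinuation (SAP 2.3); OLE doses at Weeks 0, 12, 24, 36 and 48, the last on Day 337; final visit Day 393; OLE Day 1 coincides with RECAST Day 337 (Protocol 4.1 and 5.1).

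**Assumptions, not in the documents.** Share of RECAST participants on daxdilimab 1/2 to 2/3; 0.25 to 0.5 years of daxdilimab person-time per early discontinuer; first daxdilimab dose on RECAST Day 1 for continuous participants; all 156 eligible participants enter and complete the OLE; 73% with a TEAE (borrowed from the three-dose study in Protocol 2.2.5.2 and applied flat, so the rates are illustrations only).

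**The plan's own figure.** 195 × (1 − 0.20) = 156, as stated. The complement is 39 with no OLE dose.

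**Part 1: undefined person-time**

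- RECAST-only daxdilimab recipients: 39 × 1/2 = 19.5; 39 × 2/3 = 26.
- Days by the SAP formula, OLE completer: 336 + 28 + 1 = 365 (former placebo); 336 + 336 + 28 + 1 = 701 (continuous).
- Share 1/2: 78 × 701/365.25 + 78 × 365/365.25 = 227.6 PY. Participants with a TEAE: 0.73 × 175.5 = 128.1.
- Share 2/3: 104 × 701/365.25 + 52 × 365/365.25 = 251.6 PY. Participants with a TEAE: 0.73 × 182 = 132.9.

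| Handling of RECAST-only recipients | Rate per 100 PY, share 1/2 | Rate per 100 PY, share 2/3 |
|---|---|---|
| Events kept, no person-time | 128.1/227.6 = 56.3 | 132.9/251.6 = 52.8 |
| Last daxdilimab dose in either study, 0.25 years each | 128.1/232.5 = 55.1 | 132.9/258.1 = 51.5 |
| Same, 0.5 years each | 128.1/237.4 = 54.0 | 132.9/264.6 = 50.2 |
| Dropped | 0.73 × 156/227.6 = 50.0 | 0.73 × 156/251.6 = 45.3 |

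Moving from the first row to the second and third lowers the rate by 2.1% to 4.1% (share 1/2) and 2.5% to 4.9% (share 2/3).

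**Part 2: end-date mismatch, OLE completers**

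- Former placebo: 365 days of person-time, 393 days of AE collection. Continuous: 701 and 336 + 393 = 729.
- If person-time is extended: 393/365 = 1.077 and 729/701 = 1.040. False between-group ratio 1.077/1.040 = 1.035.
- If events are truncated instead, only participants whose first TEAE falls in the last 28 days change. Under a constant hazard with 73% incidence by the final visit, incidence by the truncation date is 1 − 0.27^(365/393) = 70.4% and 1 − 0.27^(701/729) = 71.6%. The overstatement is then about 3.75% and 1.9%, a ratio of about 1.02.

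**Part 2: early OLE stoppers, person-time extended**

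For a last dose at week w, person-time is 7w + 29 days. With the early-termination (ET) visit g days after the last dose and a full 56-day safety follow-up, AE collection is 7w + g + 57 days. Averaged evenly over w = 0, 12, 24 and 36, person-time is 155 days and AE collection is 183 + g.

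- g = 84 (ET at the next due dosing visit). With 10% stopping early: (0.9 × 393 + 0.1 × 267)/(0.9 × 365 + 0.1 × 155) = 380.4/344.0 = 1.106. With 20%: 367.8/323.0 = 1.139.
- g = 0. With 10%: 372.0/344.0 = 1.081. With 20%: 351.0/323.0 = 1.087.
- So the former-placebo overstatement is about 8% to 14%. For continuous participants, add 336 days to each mean: 708.0/680.0 = 1.041 at the low end and 703.8/659.0 = 1.068 at the high end.

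**The case against.** **Intent is clear.** SAP 4.6 tabulates combined exposure on the full analysis set, which contains RECAST-only recipients. RECAST person-time was evidently meant to count, and this looks like a one-phrase omission. That stands as a description of the cause, but the text still gives no end date. The SAP's deferrals to the programming plan cover data presentation, visit windows and medication dates, not person-years.

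**Undefined is not zero.** A reader might infer that the SAP assigns these participants no person-time and so plans an inflated rate. The documents do not say that. The duration is undefined, and keeping events with no person-time is only one possible programming outcome.

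**A fixed lag after the last dose is a legitimate choice.** That is right for an exposure summary. In a rate it needs a numerator cut at the same point, and Table 4 has no cut. The size of the error does depend on the remedy: 7.7% and 4.0% hold only if person-time is extended.

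**The early-stopper figures are soft.** Protocol 7.1 asks for a prompt ET visit, so an 84-day gap is an upper case. Under Protocol 7.2, those who also withdraw consent have at most the ET visit, so assuming full follow-up overstates their gap. Both limits stand.

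**The stakes are limited.** The rate is descriptive and supplementary, and no hypothesis is tested. This also stands.

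**Conclusion.** The point holds. The wording gap in SAP 4.6 is certain: the rate in SAP 4.9.1 cannot be computed as defined for daxdilimab recipients who never received an OLE dose. They number about 20 to 26 from the discontinuation assumption alone, given the assumed allocation. The intended reading moves the pooled rate by about 2% to 5% relative to events without person-time; dropping these people would exclude early discontinuers.

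The end-date mismatch is also certain in direction. In completers the false between-group ratio is about 1.02 to 1.035, depending on the remedy. With 10% to 20% early stoppers and person-time extended, the former-placebo rate is about 8% to 14% high, assuming they complete safety follow-up.

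Two stronger readings are not supported:

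- That the primary safety results are compromised. The person-year rate is planned only for the combined summary. OLE-only summaries, simple percentages and the primary endpoint are untouched.
- That tabulating combined exposure on the full analysis set corrupts total person-years. That set already contains everyone given daxdilimab, because OLE entrants must have received RECAST treatment. Participants who received only placebo add no daxdilimab time, so only averages and percentages move.

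This should be fixed before database lock, so that the handling is not chosen after the data are seen.

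**What to change.** 1. **SAP 4.6.** In the any-daxdilimab definition, replace the last OLE dose date with the last daxdilimab dose date in either study.
2. **SAP 4.9.1.** Use one end date for events and person-time in this rate, and amend the cross-reference to SAP 4.6 to match.
   - *Preferred:* person-time to the end of AE collection in the last study the participant was in, labelled as person-years of follow-up. This keeps every collected event. Its drawbacks are that it includes time off drug and needs RECAST end-of-collection dates.
   - *Alternative:* count only TEAEs up to the last daxdilimab dose + 28 days. This needs no RECAST follow-up dates, but it drops 28 days of events for completers and up to about 112 days (141 − 29) for early stoppers. By the figure in Protocol 5.1, "3 months (approximately 5 half-lives) following the last dose of IP", one half-life is about 91/5 = 18 days, so the cut falls at about 1.5 half-lives.
3. **Optional, for consistency.** Tabulate combined exposure on the any daxdilimab analysis set.

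The cost is SAP wording and programming. The plan already pools RECAST dosing and AE data. The rules for ending AE collection in RECAST are not in these documents and would have to be taken from that study.
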